5.7 Diet/Activity/Other Considerations

No special dietary restrictions apply to this study.

5.8 Subject Withdrawal/Discontinuation Criteria

Subjects may withdraw consent at any time for any reason or be dropped from the trial at the discretion of the investigator should any untoward effect occur. In addition, a subject may be withdrawn by the investigator or the Sponsor if enrollment into the trial is inappropriate, the trial plan is violated, or for administrative and/or other safety reasons. Specific details regarding discontinuation or withdrawal procedures; including specific details regarding withdrawal from Future Biomedical Research, are provided in Section 7.1.4 – Other Procedures.

In this trial, a subject may discontinue from vaccination but continue to participate in the regularly scheduled activities, as long as the subject does not withdraw consent. Discontinuation from vaccination is permanent. Once a subject has discontinued vaccination, even though he/she continues to be monitored in the trial, he/she shall not be allowed to begin vaccination again.

A subject must be discontinued from the trial for any of the following reasons:

- The subject or legal representative (such as a parent or legal guardian) withdraws consent.
- The subject has a medical condition or personal circumstance which, in the opinion of the investigator and/or SPONSOR, places the subject at unnecessary risk through continued participation in the trial or does not allow the subject to adhere to the requirements of the protocol.
- In stage 2 (Parts I and II), any infant subject that fails to achieve adequate serologic responses, as described in Section 5.6, will be discontinued from the study.

5.9 Subject Replacement Strategy

A subject who discontinues from the trial will not be replaced.

5.10 Beginning and End of the Trial

The overall trial begins when the first subject signs the informed consent form. The overall trial ends when the last subject completes the last study-related phone-call or visit, discontinues from the trial or is lost to follow-up (i.e. the subject is unable to be contacted by the investigator).

5.11 Clinical Criteria for Early Trial Termination

Early trial termination will be the result of the criteria specified below:

The eDMC will be provided with the following stopping rules as guidance for temporarily halting or terminating the study:

If any of the following events occurs, administration of study vaccine will be temporarily discontinued until a thorough review of accumulated safety data is undertaken by the eDMC, the investigator, and /or the SPONSOR's representative.

- Death in any subject, unless the cause of death is due to obvious alternative etiology;
- Unexpected life-threatening event in any subject, unless due to obvious alternative etiology. Event should not have been previously observed with similar pneumococcal vaccines, or vaccines administered concomitantly in this study;
- Any serious adverse event, unless due to obvious etiology, with the exception of those already reported for pneumococcal conjugate vaccines or for other concomitantly administered vaccines and deemed related to those vaccines;
- Event which in the opinion of the investigator and/or safety monitoring committee contraindicates further dosing of additional subjects.

Conclusions about the overall safety of the investigational product will otherwise be determined from any SAE and solicited systemic AEs with a severe intensity rating, regardless of relationship to vaccination. The relationship to study vaccine is determined by the study investigator.

The study site and SPONSOR's personnel involved in the conduct of the study (excluding the MRL statistician and statistical programmer) will remain blinded as to the treatment allocation of the study subject.

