Safety and tolerability profiles will be carefully monitored throughout the study by the SPONSOR in accordance with standard procedures and also by an external Data Monitoring Committee (eDMC). The eDMC consists of experienced physicians and scientists in the field of infectious diseases and/or vaccines who are not employees of the SPONSOR. An eDMC charter of operations will be written and approved by the eDMC before the eDMC reviews any clinical data. The eDMC will have the responsibility of study surveillance to monitor safety outcome events and identify safety issues in order to make recommendations (including the potential to terminate the study due to a safety concern) to the Merck clinical director. The Merck clinical director will then forward the recommendations to the Executive Oversight Committee (EOC) who will decide the path forward for the trial based on the recommendations made by the eDMC. The eDMC will meet at pre-specified time points, defined in the eDMC charter, to review safety data, and a set of safety criteria proposed as stopping rules will be used by the eDMC in their evaluation of the safety data during the conduct of the study (see section 7.3.2 Data Monitoring Committee). The eDMC will review the safety data from the adult cohort (Stage 1) prior to the initiation of the small infant cohort (Stage 2 – Part I).

In order to evaluate the safety profile of V114 in infants, VRC-prompted injection-site adverse experiences (redness, swelling, hard lump [rated by size] and pain/tenderness) and VRC-prompted systemic adverse experiences (irritability, drowsiness, appetite lost, hives/welts) will be recorded for 14 days. If a hard lump at the injection site is present for 72 hours, the subject's parent/legal guardian should immediately contact the site to schedule an appointment with the study site for an evaluation within 48 hours, where the study doctor will diagnose the injection-site reaction (e.g., induration or nodule). If hives/welts (urticaria) occur, the subject's parent/legal guardian should immediately contact the site to schedule an

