7.3.2 Data Monitoring Committee

To supplement the routine trial monitoring outlined in this protocol, an external Data Monitoring Committee (DMC) will monitor the interim data from this trial. The voting members of the committee are external to the Sponsor. The members of the DMC must not be involved with the trial in any other way (e.g., they cannot be trial investigators) and must have no competing interests that could affect their roles with respect to the trial.

The DMC will make recommendations to the EOC regarding steps to ensure both subject safety and the continued ethical integrity of the trial. Also, the DMC will review interim trial results, consider the overall risk and benefit to trial participants (see Section 8.7 - Interim Analyses) and recommend to the EOC if the trial should continue in accordance with the protocol.

Specific details regarding composition, responsibilities, and governance, including the roles and responsibilities of the various members and the Sponsor protocol team; meeting facilitation; the trial governance structure; and requirements for and proper documentation of DMC reports, minutes, and recommendations will be described in a separate charter that is reviewed and approved by the DMC. The DMC will monitor the trial at an appropriate frequency, as described in the detailed DMC charter. The DMC will also make recommendations to the Sponsor protocol team regarding steps to ensure both subject safety and the continued ethical integrity of the trial.

Safety Monitoring

The eDMC will include clinicians experienced in vaccinology, infectious diseases and/or pediatrics as well as a statistician; this is in addition to the unblinded MRL statistician who will be a non-voting member of the committee.

The eDMC will be provided with the following stopping rules as guidance for temporarily halting or terminating the study:

If any of the following events occurs, administration of study vaccine will be temporarily discontinued until a thorough review of accumulated safety data is undertaken by the eDMC, the investigators, and/or the SPONSOR's representative.

- Death in any subject, unless the cause of death is due to obvious alternative etiology;
- Unexpected life-threatening event in any subject, unless due to obvious alternative etiology. Event should not have been previously observed with similar pneumococcal vaccines, or vaccines administered concomitantly in this study;

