- Any serious adverse event, unless due to obvious alternative etiology, with the exception of those already reported for pneumococcal conjugate vaccines or for other concomitantly administered vaccines and deemed related to those vaccines;
- Event in which in the opinion of the investigator and/or safety monitoring committee contraindicates further dosing of additional subjects.

Conclusions about the overall safety of the investigational product will otherwise be determined from any SAE and solicited systemic AEs with a severe intensity rating, regardless of relationship to vaccination. The relationship to study vaccine is determined by the study investigator.

The study site and SPONSOR's personnel involved in the conduct of the study (excluding the study statistician and statistical programmer) will remain blinded as to the treatment allocation of the study subject. The eDMC, unblinded statistician, and statistical programmer will be unblinded throughout the study. The EOC will be blinded, however it may be unblinded to evaluate the eDMC recommendations.

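### The serious-adverse-event pause criterion has a different scope in protocol 5.11 and 7.3.2, and the two texts must be reconciled

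*Combined protocol and SAP*

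**What the plan says.** Section 5.11 (Clinical Criteria for Early Trial Termination) and the Safety Monitoring part of 7.3.2 (Data Monitoring Committee) each set out a four-bullet list of events. The lead-in in 7.3.2 is "The eDMC will be provided with the following stopping rules as guidance for temporarily halting or terminating the study", and 5.11 opens its list in the same terms. In both sections the next sentence says that study vaccination will be paused, pending a safety review, if any listed event occurs.

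The SAE bullet in 5.11 begins "Any serious adverse event, unless due to obvious etiology, with the exception of those already reported for pneumococcal conjugate vaccines". In 7.3.2 it begins "Any serious adverse event, unless due to obvious alternative etiology, with the exception of those already reported for pneumococcal conjugate vaccines". Both continue with the same second limb, "or for other concomitantly administered vaccines and deemed related to those vaccines".

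The other bullets bear on how far this difference reaches. In 5.11 the death bullet is "Death in any subject, unless the cause of death is due to obvious alternative etiology". The bullet on unexpected life-threatening events also exempts only an obvious alternative cause, and adds "Event should not have been previously observed with similar pneumococcal vaccines, or vaccines administered concomitantly in this study". The last bullet is "Event which in the opinion of the investigator and/or safety monitoring committee contraindicates further dosing of additional subjects". Section 7.3.2 carries all three with the same substance.

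Section 4.2.3.2 says that "stopping rules will be used by the eDMC in their evaluation of the safety data during the conduct of the study (see section 7.3.2", so it directs the reader to 7.3.2. It also says that a charter will be approved before the eDMC sees any data. The charter is not among the documents reviewed.

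**The concern.** The missing word changes which events fall under the rule. If only an obvious alternative cause exempts an SAE, then an SAE plainly due to study vaccine remains a trigger, subject to the already-reported exception. If any obvious cause exempts it, that same event is not a trigger under the SAE bullet.

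The rule bears on continued dosing of new formulations in healthy adults and then in infants, with enrolment staged behind safety reviews. Section 5.11 carries the title on early termination and does not send its reader to 7.3.2. Both sections name the investigator or investigators and the sponsor's representative, as well as the eDMC, as possible reviewers of a pause. Someone working from 5.11 and someone working from 7.3.2 could therefore reach different answers on whether the same event calls for an automatic pause.

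**Working it through.** No arithmetic applies to the main point. Setting the two lists side by side:

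| Element | 5.11 | 7.3.2 |
|---|---|---|
| Status | Guidance given to the eDMC | Same |
| Consequence | Vaccination paused pending review | Same |
| Death | Exempt only for an obvious alternative cause | Same |
| Unexpected life-threatening event | Exempt for an obvious alternative cause; must not have been seen before with similar or concomitant vaccines | Same |
| SAE, exemption by cause | Any obvious cause | Obvious alternative cause only |
| SAE, already-reported exception | Present | Same |
| Opinion-based bullet | Present | Same in substance |

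Only one row differs in substance. The steps below show which events it affects.

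1. Take an SAE whose cause is not obvious, or is obviously something other than study vaccine. Both SAE bullets treat it alike, so there is no difference.
2. Take an SAE obviously caused by study vaccine. The 5.11 bullet exempts it by cause. The 7.3.2 bullet does not.
3. Remove events caught elsewhere. A death obviously due to vaccine triggers both lists through the death bullet. An unexpected, not previously observed life-threatening event obviously due to vaccine triggers both through its own bullet.
4. Remove events covered by the already-reported exception, which exempts them in both lists.
5. What remains is an SAE obviously due to study vaccine that is either neither fatal nor life-threatening, or life-threatening but outside the second bullet because it was expected or previously observed, and that the already-reported exception does not cover. With the opinion bullet set aside, 5.11 does not call for a pause and 7.3.2 does.

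The width of step 4 depends on how the exception is read. The condition about being deemed related may qualify both pneumococcal conjugate and concomitant vaccines, or only the concomitant ones. On the first reading, an SAE already reported for conjugate vaccines but not deemed related stays in the gap. On the second, it is exempt in both lists. On either reading, a vaccine-caused SAE that has not been reported before and is caught by no other bullet remains in the gap. The gap therefore exists whichever reading is taken, but its exact extent is not fixed by the text. No count of affected event types is offered, because it would depend on that choice.

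**Minor note on the extra licensed dose.** Section 4.3 places the dose between 9 and 12 months of age. Section 5.6 ties it to the earliest opportunity once serology is available, with no age limits. From the visit windows in 6.0, with a month taken as 365.25/12 = 30.44 days:

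- Earliest postdose 3 draw: 6 × 30.44 + 28 = 210.6 days (6.9 months).
- Latest postdose 3 draw: 7 × 30.44 − 1 + 42 = 254.1 days (8.3 months).
- All on-schedule results fall at 9 months (273.9 days) or later if turnaround is at least 273.9 − 210.6 = 63.3 days.
- All fall at 12 months (365.25 days) or earlier if turnaround is at most 365.25 − 254.1 = 111.2 days.

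At an assumed turnaround of about 64 to 111 days, both statements can be met for every on-schedule infant. Outside that range, some or all results would fall outside the 4.3 window. The documents give no turnaround, so they show two wordings but not a conflict in practice.

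**The case against.** The best case against the point is that this is a copying slip with little practical effect. Much of that stands.

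- The death and life-threatening bullets in 5.11 both say *alternative*. On the literal reading, the already-reported exception in the same sentence would be largely redundant.
- The two lists differ in other small, plainly editorial ways, which fits imperfect duplication.
- Section 4.2.3.2 names 7.3.2 as the place for the stopping rules.
- The rules are guidance, and the last bullet allows a pause on the opinion of the investigator or safety committee.
- Under 7.2.3.1, SAEs from randomization to 30 days after the last vaccination reach the sponsor within 24 hours, related or not. Both sections also base overall safety conclusions on any SAE regardless of relationship.

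These points make a dropped word likely and limit the risk. None of them amends 5.11. The opinion bullet makes discretionary what the SAE bullet in 7.3.2 makes automatic, and 24-hour reporting informs the sponsor without pausing dosing. The sentence on the pause is worded as something that will happen, although the list is called guidance.

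A reader might infer that the plan would let vaccination continue after SAEs known to be caused by the vaccine. The documents do not support that. Section 7.3.2 says otherwise, deaths and unexpected, not previously observed life-threatening events trigger both lists, and a pause on opinion is always open.

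A reader might also infer that 4.3 and 5.6 impose incompatible timings for the extra dose. That is not shown either. It depends on an unstated turnaround, 4.3 refers to 5.6 for details, and 2.1 and 5.6 place the dose outside the protocol.

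**Conclusion.** The point holds as a discrepancy in an operative safety rule. Sections 5.11 and 7.3.2 state the same SAE pause criterion with different scope, and as written they cannot both be the rule. This rests on the text alone and needs no assumed figure.

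Its extent is limited to SAEs obviously due to study vaccine that no other bullet and no already-reported exception covers. How often such events would occur cannot be estimated from the documents, and whether the eDMC charter repeats either wording is unknown. The practical risk is small, but correction costs almost nothing and the rule concerns continued dosing. It should therefore be corrected rather than left to inference. No view is taken here on which wording is right.

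The difference between 4.3 and 5.6 is a minor wording matter. It would become a conflict only if assay turnaround fell outside the range shown above.

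**What to change.** Reconcile 5.11 and 7.3.2 so that the SAE pause criterion is stated once, with the other section cross-referring to it, and check that the eDMC charter carries the same text. While doing so, make clear whether the deemed-related condition in the already-reported exception applies to both classes of vaccine or only to concomitant ones. The sponsor's clinical team and the eDMC decide what is intended.

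As a minor item, reconcile 4.3 and 5.6 so that the timing of the extra licensed dose is stated one way. That choice also belongs to the clinical team.

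The cost is a word or a cross-reference in 5.11 or 7.3.2, a short clarification of the exception, a phrase in 4.3 or 5.6, and a check of the charter. Sample size, endpoints and analyses do not change.

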6.0 TRIAL FLOW CHART

Adult Cohort		
	Visit Number:	1
	Visit Timing:	Day 1 DOSE 1
	Visit Window:	+ 14 days
Administrative Procedures		
Informed Consent ^a		X
Informed Consent for Future Biomedical Research (FBR) ^b		X
Inclusion/Exclusion Criteria		X
Subject Identification Card		X
Urine Pregnancy Test ^c		X
Medical History		X
Concomitant Medication Review		X
Vaccination Allocation/Randomization		X
Study Vaccine Administration ^d		X
Provide Electronic Vaccination Report Card (VRC)		X
Review VRC data		X
Clinical Procedures/Assessments		
Targeted Physical Examination (optional, per investigator's discretion; perform if needed to assess inclusion/exclusion criteria)		X
Obtain Oral Temperature		X
30 Minutes Postvaccination Observation Period		X
Adverse Experience Monitoring ^e		X
Assess for Serious Adverse Experiences ^e		X
Laboratory Procedures/Assessments		
Collect blood samples for immunogenicity assays (40 mL) ^{f,g}		X
Collect Buccal Swabs for Future Biomedical Research ^b		X

Adult Cohort		
Visit Number:	1	2
Visit Timing:	Day 1 DOSE 1	30 days after Visit 1
Visit Window:		+ 14 days

a. Consent must be obtained prior to any study procedures.
 
b. Informed consent for future biomedical research samples must be obtained before the collection of the buccal swab DNA samples. Buccal swab DNA samples for analysis should be obtained prior to the vaccination, on Day 1, on randomized subjects only, or at a later date as soon as the informed consent is obtained.
 
c. Urine pregnancy test (sensitive to 25 IU β-hCG) must be done prior to vaccination in women of reproductive potential
 
d. In order to avoid bias, the unblinded study personnel will have no further contact with study subjects for any study-related procedures/assessments following administration of the study vaccines. This includes all safety follow-up procedures. Contact between subjects and unblinded study personnel after vaccination administration is strictly prohibited.
 
e. Adverse experiences (serious and non-serious) are to be reported from Day 1 to 14 days following the vaccination. Serious Adverse Experiences are to be reported throughout the subject's study participation.
 
f. Leftover serum samples collected from the main study will be stored for future use if the FBR consent is signed.
 
g. Collect blood prior to vaccination.
		

Infant Cohort						
Visit Number:	1 ^a	2 ^a	3	4	5	6
Visit Timing:	Age:~2 months DOSE 1	Age:~4 months DOSE 2	Age:~6 months DOSE 3	30 days after Visit 3	Age:~12 to 15 months DOSE 4	30 days after Visit 5
Visit Window:	≥42 days of age to ≤90 days of age	4 months of age to 1 day prior to 5 months of age	6 months of age to 1 day prior to 7 months of age	28 to 42 days PD3	12 months of age to 1 day prior to 16 months of age	28 to 42 days PD4
Administrative Procedures						
Informed Consent ^b	X					
Informed Consent for Future Biomedical Research (FBR) ^c	X					
Inclusion/Exclusion Criteria	X					
Subject Identification Card	X					
Medical History	X					
Update Medical History (New condition not already recorded as medical history or adverse experiences)		X	X	X	X	X
Concomitant Medication Review	X	X	X	X	X	X
Vaccination Allocation/Randomization	X					
Study Vaccine Administration ^d	X	X	X		X	
Childhood Vaccines ^e	X	X	X		X	
Provide Electronic Vaccination Report Card (VRC)	X					
Review VRC data ^f		X	X	X		X
Clinical Procedures/Assessments						
Full Physical Examination	X					
Targeted Physical Examination		X	X		X	
Obtain Rectal Temperature ^g	X	X	X		X	
30 Minutes Postvaccination Observation Period	X	X	X		X	
Adverse Experience Monitoring ^h	X	X	X	X	X	X
Assess for Serious Adverse Experiences ⁱ	X	X	X	X	X	X
Laboratory Procedures/Assessments						
Collect blood samples for immunogenicity assays (4-5 mL) ^{h, i}				X	X	X
Collect Buccal Swabs for Future Biomedical Research ^c	X					

Infant Cohort						
Visit Number:	1 ^a	2 ^a	3	4	5	6
Visit Timing:	Age:~2 months DOSE 1	Age:~4 months DOSE 2	Age:~6 months DOSE 3	30 days after Visit 3	Age:~12 to 15 months DOSE 4	30 days after Visit 5
Visit Window:	≥42 days of age to ≤90 days of age	4 months of age to 1 day prior to 5 months of age	6 months of age to 1 day prior to 7 months of age	28 to 42 days PD3	12 months of age to 1 day prior to 16 months of age	28 to 42 days PD4

a. For Visits 1 and 2, study coordinator should review the electronic Vaccination Report Card (VRC) in the vendors database at 14 days postvaccination (0 to plus 5 day window) and call the parent/legal guardian if there is a need to address questions (document phone call in study chart). The site will review VRC with parent/legal guardian at next visit.

b. Consent must be obtained prior to any study procedures.

c. Informed consent for future biomedical research samples must be obtained before the collection of the buccal swab DNA samples. Buccal swab DNA samples for analysis should be obtained prior to the vaccination, on Day 1, on randomized subjects only, or at a later date as soon as the informed consent is obtained.

d. In order to avoid bias, the unblinded study personnel will have no further contact with study subjects for any study-related procedures/assessments following administration of the study vaccines. This includes all safety follow-up procedures. Contact between subjects and unblinded study personnel after vaccination administration is strictly prohibited.

e. Concomitant (or routine pediatric) vaccines are to be given according to recommended schedule. Any injectable concomitant vaccines provided at the visit must be given after the study vaccine and in a separate limb, may be given during the 30-minute observation period, and do not require additional observation time.

f. Adverse experiences (serious and non-serious) are to be reported from Day 1 to 14 days following each vaccination. Serious Adverse Experiences are to be reported throughout the subject's study participation.

g. Pre-vaccination temperatures taken by study staff at Visits 1, 2, 3 and 5. Parent/legal guardian to measure and record rectal temperature per VRC instructions.

h. Leftover serum samples collected from the main study will be stored for future use if the FBR consent is signed.

i. Collect blood prior to vaccination.

